12.5.3.3 Amount of RBCs infused after IMP until End of Surgery

The amount (volume in mL and units [bags]) of RBCs (allogeneic and autologous) infused after start of first IMP administration until the end of surgery will be summarized by treatment arm.

An ANOVA analysis will be performed with the amount of RBCs required as the dependent variable and the predictive blood loss (> 1,000 mL to \leq 2,000 mL and > 2,000 mL) as a covariate. The least square means and difference in least square means will be presented with the corresponding 95% confidence intervals and 2-sided p-value. This will be repeated by surgery type.

In addition, a subgroup analysis of the amount of RBCs will be performed for the FAS. Subgroups are predictive blood loss as well as spinal and abdominal surgery. The amount of RBCs will be analyzed using an ANOVA for each subgroup. The least square means and difference of least square means together with 95% confidence intervals and p-values for each subgroup will be presented.

12.5.3.4 Post-operative Blood Loss

The post-operative blood loss in the first 24 hours is the blood loss from end of surgery until 24 hours after end of surgery. This secondary efficacy endpoint will be descriptively summarized by treatment arm.

An ANOVA analysis will be performed with the post-operative blood loss in the first 24 hours as the dependent variable and the predictive blood loss (> 1,000 mL to \leq 2,000 mL and > 2,000 mL) as a covariate. The least square means and difference (BT524 versus FFP/cryoprecipitate) in least square means will be presented with the corresponding 95% confidence intervals and 2-sided p-value. This will be repeated by surgery type.

A box-whisker plot for post-operative blood loss will be generated for both treatment arms.

In addition, a subgroup analysis of the post-operative blood loss in the first 24 hours will be performed for the FAS. Subgroups are spinal and abdominal surgery. The post-operative blood loss will be analyzed using an ANOVA for each subgroup. The least square means and difference of least square means together with 95% confidence intervals and p-values for each subgroup will be presented.

Post-operative blood loss will be listed for the FAS.

12.5.3.5 Proportion of Subjects with Rebleeds

The proportion of subjects with rebleeds will be compared between the treatment arms using a CMH approach stratified by predictive blood loss (> 1,000 mL to \leq 2,000 mL and > 2,000 mL). The number and

percentage of subjects with a rebleed will be presented with corresponding 95% confidence intervals. The estimated treatment effect (i.e., the difference in rebleed rate between the treatment arms, BT524 – standard treatment (FFP/cryoprecipitate)), corresponding 95% confidence interval, and 2-sided p-value for the difference will be presented. The descriptive summary of the number of rebleeds will also be presented by treatment arm.

Analysis will be repeated for spinal and abdominal surgery.

Post-operative rebleeds will be listed for the FAS.

12.5.3.6 Length of Hospital Stay after Surgery

Subjects without a date of discharge (i.e., hospitalization ongoing) at Day 36 will be classified into > 36 days. The frequency of subjects whose length of hospital stay falls in the following categories are presented: 1-7, 8-14, 15-21, 22-28, 29-36, > 36 days.

The length of hospital stay after surgery will be summarized descriptively by treatment arm for those subjects, who had a day of discharge until closing visit. The details of surgery date, discharge or ongoing hospital stay, as well as length of hospital stay will be listed for the FAS.

Analysis will be repeated for spinal and abdominal surgery.

12.5.3.7 In-hospital Mortality

The number and percentages of subjects who died during their hospital stay will be presented with corresponding 95% confidence intervals of death rate by treatment arm using the Clopper-Pearson Method.

Analysis will be repeated for spinal and abdominal surgery.

The details of mortality during hospital stay will be listed for the FAS.

12.5.3.8 Overall Mortality

The number and percentages of subjects who died will be presented with corresponding 95% confidence intervals of death rate by treatment arm using the Clopper-Pearson Method.

The details of overall mortality will be listed for the FAS.

12.6 Safety Analyses

All safety analyses will be based on the SAF.

12.6.1 Adverse Events

Adverse events will be coded using the most updated version of the MedDRA® dictionary.

Adverse events occurring during or after the administration of study medication are TEAEs. If a partially missing AE start date is imputed, the imputed date will be used to assess if the AE is treatment emergent. If AE start date is completely missing and AE end date/time is after IMP start date/time or if it is completely missing, then it is a TEAE. All other AEs are regarded non-treatment emergent.

The search criteria for the adverse events of special interest are specified in the table below:

AESI	Search Criteria
Thrombosis or TEE	SMQ: Embolic and thrombotic events (narrow)
Relevant bleeding complication	All AESIs ticked as AESI, but not falling under categories "Thrombosis or TEE" or "Suspicion of transmission of infective agents (viral safety)"
Suspicion of transmission of infective agents (viral safety)	Preferred terms: "transmission of infectious agent via product" and "suspected transmission of infectious agent via product"

Adverse events related to Hypersensitivity/anaphylactic reactions/anaphylactic shock will be selected by using the following criteria: SMQ: Hypersensitivity, (narrow), Anaphylactic reaction (narrow), and Anaphylactic shock conditions (narrow).

Adverse events related to bleeding related ischaemic events will be selected by using the following criteria: SMQ: Ischaemic heart disease: Myocardial infarction (narrow), Other ischaemic heart disease (narrow); Ischaemic colitis (broad); Ischaemic central nervous system vascular conditions (narrow); Embolic and thrombotic events, arterial (narrow); Embolic and thrombotic events, venous (narrow); PT: Peripheral ischaemia; Ischaemia; Gastric ischaemia; Hepatic ischaemia; Ischaemic contracture of the left ventricle; Dry gangrene; Ischaemic gastritis; Ischaemic limb pain; Necrosis ischaemic; Spleen ischaemia; Uterine ischaemia.

If a serious adverse event (SAE) occurs in a subject after the period of observation, i.e., after the last study visit, and is considered by the investigator to be related to the study medication, this should still be recorded as a SAE. If the eCRF has been closed for the subject, the investigator should contact the sponsor to determine how to report the SAE.

The total number and percentage of subjects reporting at least one AE and the absolute count of AEs will be tabulated for each treatment, treatment arm and overall once for the overall trial population and separately by type of surgery (spinal and abdominal surgery), sex and race. The initial summary will also provide a breakdown of the following:

- Any AE
- Any non-severe AE
- Any TEAE
- Any NTEAE
- Any non-serious TEAE
- Any non-severe TEAE
- Any treatment-related TEAE
- Any severe AE
- Any severe TEAE
- Any severe treatment-related TEAE
- Any SAE
- Any serious TEAE
- Any serious treatment-related TEAE
- Any AESI
- Any treatment-emergent AESI
- Any treatment-emergent treatment-related AESI
- Any AE leading to discontinuation from study
- Any TEAE leading to discontinuation from study

- Any treatment-related TEAE leading to discontinuation from study
- Any AE with outcome of death
- Any TEAE with outcome of death
- Any treatment-related TEAE with outcome of death
- Any TEAE of special interest
 - Thrombosis or TEE
 - Suspicion of transmission of infective agents
 - Relevant bleeding complication
- Any TEAE of Hypersensitivity/ anaphylactic reactions/ anaphylactic shock
- Any TEAE of Bleeding related ischaemic events

The number of events, number and percentage of subjects reporting AEs will be tabulated (as well for causality and maximum severity) in the following way once for the overall population, and separately by type of surgery (spinal and abdominal surgery) and sex in the following:

- Treatment-emergent AEs by system organ class and preferred term
- Serious treatment-emergent AEs by system organ class and preferred term
- Causally related TEAE by system organ class, preferred term and maximum severity
- Not Causally related TEAE by system organ class, preferred term and maximum severity
- Causally related Serious TEAE by system organ class, preferred term and maximum severity
- Not Causally related Serious TEAE by system organ class, preferred term and maximum severity

The number of events, number and percentage of subjects reporting AEs will be tabulated (as well for causality and maximum severity) in the following way once for the overall population, and separately by type of surgery (spinal and abdominal surgery) in the following:

- Non-treatment emergent AEs by system organ class and preferred term (will not be tabulated for maximum severity or causality)
- Treatment-emergent AEs by system organ class and preferred term of Hypersensitivity/ anaphylactic reactions/ anaphylactic shock
- Treatment-emergent AEs by system organ class and preferred term of Bleeding Related Ischaemic Events
- Treatment-emergent AEs by system organ class and preferred term leading to study discontinuation (will not be tabulated for maximum severity, causality or separately by type of surgery)
- Treatment-emergent AEs by system organ class and preferred term leading to death (will not be tabulated for maximum severity or separately by type of surgery)
- Treatment-emergent AEs by system organ class and preferred term leading to hospitalization (will not be tabulated for maximum severity or causality)

The following AESI categories (only treatment-emergent adverse events) will be presented by system organ class and preferred term for the overall population, and separately by type of surgery and sex. They are repeated for maximum severity and causality for overall and surgery type only.

- Adverse events of special interest:
 - Thrombosis or TEE
 - Suspicion of transmission of infective agents (presented only for the overall population and for causality)

Relevant bleeding complication

Listings will be produced for all AEs (including non-treatment emergent adverse events) reported in the eCRF for the All Subjects Enrolled Set.

In the listing, time to onset will be presented. Time to onset of the adverse event is defined as start date/time of adverse event – date/time of first study drug administration.

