# 9.3.3 Period of Observation

The period of observation for collection of AEs extends from the time the subject signs the ICF until the last study visit (Day 36), which is scheduled 5 weeks after the day of the surgery (day of IMP administration).

Abnormal, clinically relevant findings or observations made prior to signature of informed consent are to be recorded as medical history/concomitant disease but not as AEs.

AEs (including any change in severity or trait of the concomitant disease/ medical history) occurring in the pre-treatment period between signature of informed consent until first administration of study medication are non-treatment emergent AEs (NTEAEs).

AEs (including any change in severity or trait of the concomitant disease/ medical history) occurring from the administration of study medication until the subject's last study visit are treatment-emergent AEs (TEAEs).

If an SAE occurs in a subject after the period of observation, i.e., after the last study visit, which is considered by the investigator to be related to the study medication, this should be recorded as SAE and follow the immediate reporting process for SAEs as described

in Appendix 2. If the eCRF has been closed for the subject, the investigator should contact the sponsor to determine how to report the SAE (see also section 7.4).

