#### • Intensity/Severity

Refers to the extent to which an AE affects the subject's daily activities. Severity will be categorized according to the following criteria:

Mild	The AE does not interfere with the subject's routine activities.
Moderate	The AE interferes with the subject's daily routine, but usual routine activities can still be carried out.
Severe	The AE results in inability to perform routine activities.

 Table: Adverse Event Severity

**Severe vs. Serious:** The severity is used to describe the intensity of an event. This is not the same as seriousness, which is based on subject/event outcome or action criteria usually associated with events that pose a threat to subject's life or functioning. Seriousness, not severity, serves as the guide for defining regulatory reporting obligations.

Example: While an event may be of "severe" intensity, it may be of relatively minor medical significance, such as severe headache. On the other hand, a myocardial infarction would be usually regarded as serious, even if its intensity is "mild".

If formal severity classifications are used, such as the NCI CTC classification used in oncology studies, provisions should be made regarding the reporting of events of defined grading (e.g.  $\geq$  3) as serious.

**AEs with changes in severity:** If an AE changes in severity, this will be captured as one AE with the highest severity grade recorded.

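### The TEAE definition has no worsening clause: an adverse event that starts before first IMP and worsens afterwards reads as non-treatment-emergent and leaves the TEAE and AESI category tables, though not the all-AE overview or the listings

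*SAP*

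**What the plan says.** SAP 12.6.1 gives the classification rule: "Adverse events occurring during or after the administration of study medication are TEAEs". The start date is the deciding variable: "If a partially missing AE start date is imputed, the imputed date will be used to assess if the AE is treatment emergent". An event with no start date at all is a TEAE if its end is after the start of IMP or is also missing. The remainder is closed off with "All other AEs are regarded non-treatment emergent".

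Protocol Appendix 1, under Intensity/Severity, sets the recording rule: "If an AE changes in severity, this will be captured as one AE with the highest severity grade recorded".

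Protocol 9.3.3 puts events arising between consent and first IMP in the non-treatment-emergent class and events from IMP to the last visit in the treatment-emergent class. In both it includes changes in severity of a concomitant disease or medical history. It does not mention worsening of an AE already on record, and the SAP carries over none of this wording.

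On output, SAP 12.6.1 plans a non-treatment-emergent table by system organ class and preferred term only, without maximum severity or causality. For special-interest events it states: "The following AESI categories (only treatment-emergent adverse events) will be presented".

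**The concern.** A TEAE definition commonly covers two groups: events that start on or after treatment, and events that start earlier and get worse on treatment. The SAP has only the first.

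In many trials the second group is small. Here the first dose falls in the middle of an operation on a patient who is bleeding or expected to bleed. SAP 6.1 places the trigger at about 1 L of bleeding in spine surgery, and at a prediction of more than 2 L roughly an hour into PMP surgery. Hypotension, tachycardia or anaemia can plausibly begin before the dose and deepen after it. Such deterioration is of direct safety interest for a haemostatic product. Protocol 9.3.1 accordingly defines the special-interest category of relevant bleeding complication by changes that occur after IMP. If the tables assign such an event to the pre-treatment period, the definition and the tabulation of that category disagree.

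**Working it through.** No plan figure bears on this point and no arithmetic applies. The check follows one event through the rules. Take hypotension reported as an AE after the start of surgery and before first IMP, graded moderate, still present at dosing and severe afterwards.

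1. Recording (Protocol Appendix 1). One record, highest grade severe. Nothing creates a second onset, so the start stays before first IMP. This step is an inference from the one-record rule; no sentence states it literally.
2. Classification (SAP 12.6.1). The start precedes IMP, so the event is not a TEAE and falls to the residual class.
3. Tables lost (SAP 12.6.1). It is absent from the TEAE and severe-TEAE overview rows, from the TEAE tables by system organ class and preferred term with their causality and maximum-severity versions, and, if ticked as AESI, from the AESI category tables.
4. Tables kept (SAP 12.6.1 and 12.6.2). It counts in the overview rows for any AE, any NTEAE and any severe AE and, where it qualifies, any SAE, any AESI and any AE with fatal outcome. It appears in the AE listing with time to onset and, if serious, in the SAE listing.

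The same clinical course is classified differently under other recording circumstances:

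| Circumstance | Governing text | Class |
|---|---|---|
| Start documented before first IMP, worsens after, one record | Appendix 1; SAP 12.6.1 | NTEAE |
| Start time missing, date is the day of dosing | SAP 8.5.1 sets the time to that of first IMP | TEAE |
| Site enters the deterioration as a new AE | Protocol 9.2.1.3, 9.3.1 | TEAE |
| Condition present before consent, worsens after IMP | Protocol 9.2.1.2, 9.3.3 | TEAE |
| Event stops before dosing and restarts after | Appendix 1, onset and end date | TEAE |

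Only the first row goes to the non-treatment-emergent class, although it is the best documented. The second row shows the contrast: a missing start time on the day of dosing leads to treatment-emergent, while a known start with later worsening does not. The SAP is also cautious elsewhere: for an AE starting on or after IMP, missing severity becomes severe (8.4.1) and missing causality becomes related (8.4.2). An omission is therefore more likely than a deliberate choice.

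A further consequence follows from step 1. If only the highest grade is kept, neither the grade before dosing nor the time of worsening is on the record as the protocol describes it. A worsening clause in the SAP alone could not be programmed from such data.

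**The case against.** The strongest reply is that the protocol already directs much post-dose deterioration into new AE records. Protocol 9.2.1.3 has vital signs recorded before IMP, at 15 and 90 minutes after its start and at end of surgery, and asks for an AE when the change from pre-treatment values is clinically significant. Section 9.3.1 includes aggravation in the definition of an AE, 9.3.2 makes a complication a separate AE, and 9.3.4 has laboratory values judged against pre-treatment values. The bleeding AESI is post-dose by definition. Appendix 1 leaves worsening of the disease under study to the efficacy parameters unless stated conditions are met, and blood loss after the decision to treat is the primary endpoint.

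Much of this stands. It narrows the gap to worsening under the same term of an event that began after consent and before first IMP. It does not close the gap, because a site following the one-record rule and a site following the aggravation wording would enter the same course differently, and the SAP would classify the two entries differently.

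Three stronger readings are tempting and should not be drawn:

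- A reader might infer that these events vanish from the severity and AESI output. They do not; step 4 lists where they remain.
- A reader might multiply an assumed frequency of pre-dose events by an assumed share that worsens, and call the product the share of subjects missing from the TEAE tables. Neither input is in the documents. The product would also be the share with such an event: a subject leaves a subject-level TEAE row only if no other event of theirs qualifies for it.
- A reader might extend the point to non-serious events that become serious. Appendix 1 announces a separate onset and end date rule for these, but its content is not legible in the copy reviewed, so that case cannot be judged.

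**Conclusion.** The point holds in a limited form. Taken together, SAP 12.6.1 and Appendix 1 place post-dose worsening of an AE with onset between consent and first IMP in the non-treatment-emergent class. They remove it from the TEAE rows, from the tables by severity and causality, and from the AESI category tables. The event stays visible in the all-AE overview rows and the listings, but these do not show what worsened after treatment by preferred term, severity or causality.

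This rests on two assumptions: that the single record keeps its original start, and that sites apply the one-record rule rather than opening a new AE. The protocol is in tension with itself on the second. The number of events affected and any imbalance between arms cannot be derived from the documents. The primary efficacy analysis is untouched. The correction is worth making before database lock because first IMP is given mid-surgery and one special-interest category is defined by what happens after it.

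**What to change.** **SAP 12.6.1.** Define a TEAE as an AE with onset at or after the start of first IMP, or with earlier onset and an increase in severity after the start of first IMP.

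**Protocol Appendix 1 and eCRF guideline.** Reconcile the one-record rule with the aggravation wording, so that worsening after first IMP is entered either as a new AE or with a date and time of worsening on the existing record.

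**Records already entered.** Query AEs with onset before first IMP that were ongoing at first IMP. Reclassify only those where worsening after the start of first IMP is confirmed. Where the timing cannot be established, count the event as treatment-emergent in a sensitivity table. Reclassifying every such record that is graded severe, serious or ticked AESI would be wrong, because it would include events that had already reached that state before dosing.

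**Cost.** One SAP sentence, a minor protocol change under Protocol 13.7 with the matching eCRF guideline text, a small set of queries, and slightly higher TEAE counts. SAP 3.0 leaves room for this, since the plan is finalised only before database lock.

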# • Adverse Event of Special Interest (AESI)

An AE of special interest (serious or non-serious) is one of scientific and medical concern specific to the sponsor's IMP or development program, for which ongoing monitoring and immediate communication by the investigator to the sponsor may be appropriate. Such events may require further investigation in order to characterize and understand them. Reporting requirements are detailed in Appendix 2.

The following AEs have been defined as AESI for this study:

- Thrombosis or TEE
- Relevant bleeding complication:

Relevant changes of a vital sign or laboratory value (e.g. severe tachycardia, severe hypotension, hypovolemic shock, severe anemia) occurring after IMP administration, during and/or after surgery that require immediate corrective action/treatment and are caused by bleeding.

Note: Corrective treatment includes e.g. the administration of unplanned blood products or other drugs.

• Suspicion of transmission of infective agents (viral safety).

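### The SAP counts every ticked AESI left over after two coded searches as a bleeding complication, without the bleeding criterion that the protocol requires

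*SAP*

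**What the plan says.** Protocol 9.3.1 names three AESIs: thrombosis or TEE, relevant bleeding complication, and suspected transmission of infective agents. It defines the bleeding one positively. The definition opens with "Relevant changes of a vital sign or laboratory value", places the change after IMP administration, and covers only changes "that require immediate corrective action/treatment and are caused by bleeding".

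SAP 12.6.1 replaces these definitions with a table, introduced by "The search criteria for the adverse events of special interest are specified in the table below":

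- Thrombosis or TEE is found by one narrow standardised MedDRA query (SMQ) for embolic and thrombotic events.
- Viral safety is found by two preferred terms, one of which is "suspected transmission of infectious agent via product".
- Relevant bleeding complication is "All AESIs ticked as AESI, but not falling under categories" of the other two kinds.

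The categories appear in the adverse event overview and again in their own tables: "The following AESI categories (only treatment-emergent adverse events) will be presented by system organ class and preferred term". The bleeding category is also split by type of surgery and sex, and by severity and causality. SAP 7.2.3 lists relevant bleeding complications as a safety parameter. SAP 4.1, which sets out the changes from the protocol, does not mention this one.

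**The concern.** The bleeding category is defined by what it is not. Whether an event was caused by bleeding plays no part in deciding whether it enters that row. The tick is also used unevenly: the bleeding category depends on it entirely, while the thrombosis and viral categories do not use it.

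Readers will compare these three rows between arms. BT524 is given to control bleeding, and the frequency and severity of thrombosis and TEE is a named secondary safety endpoint. What is at stake is whether each row's total counts what its label says.

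**Working it through.** The plan states no figure on this point, so the check is one of logic, followed by a simple calculation of size.

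**Step 1: the rule as written.** Let S = 1 if the coded term is in the narrow SMQ, V = 1 if it is one of the two viral preferred terms, and T = 1 if the event is ticked as an AESI. No term is taken to be in both searches.

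| S | V | T | Category under SAP 12.6.1 |
|---|---|---|---|
| 1 | 0 | 0 or 1 | Thrombosis or TEE |
| 0 | 1 | 0 or 1 | Viral safety |
| 0 | 0 | 1 | Relevant bleeding complication |
| 0 | 0 | 0 | No AESI category |

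**Step 2: compare with Protocol 9.3.1.** Let B = 1 if the event was caused by bleeding and needed immediate correction. B appears nowhere in the table. Two kinds of error follow:

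- S = 0, V = 0, T = 1, B = 0: counted as bleeding, but not bleeding.
- S = 0, V = 0, T = 0, B = 1: a bleeding complication that is not counted.

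**Step 3: can these arise in this trial?**

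- *Viral.* Protocol 9.2.1.4 has HIV, hepatitis B and hepatitis C serology at screening and closing, and makes clinically relevant abnormal laboratory values adverse events. Protocol 9.3.2 asks for a diagnosis where possible. Any suspicion of transmission is an AESI. A ticked event recorded and coded as the infection or the serology finding has S = 0 and V = 0 and goes to bleeding. If it is coded to one of the two listed terms, it is filed correctly.
- *Ticked in error.* An allergic reaction, for instance, is not among the three AESIs. If it were ticked, it would be labelled bleeding.
- *Unticked bleeding.* Severe tachycardia or anaemia caused by bleeding, entered as an adverse event without the tick, is lost to the category.
- *Thrombosis.* A ticked thrombotic event would go to bleeding only if its term lay outside the narrow SMQ. The documents do not list the SMQ's terms, so this route is conditional and has no documented example.

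**Step 4: is there a later correction?** The blind data review meeting (BDRM) is given protocol deviations, missing data, model assumptions and possible further subgroups (SAP 8.4, 9.4, 10.0, 12.2 and 12.5.1). Neither document describes a step that re-sorts ticked AESIs falling outside the two searches.

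**Step 5: size of one misfiled subject.**

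- With 100 subjects per arm: 1/100 = 1.0 percentage point.
- With the roughly 220 randomised subjects of SAP 6.2: 220/2 = 110 per arm, and 1/110 = 0.9 percentage points.
- By type of surgery, for illustration: if only the 40 PMP subjects named for the second interim analysis were enrolled, 40/2 = 20 per arm and 1/20 = 5 percentage points. The final PMP number is not fixed in the documents.

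The documents give no AESI rates, so the number of misfiled events cannot be estimated.

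**The case against.** The residual rule has a rationale. The protocol has exactly three AESIs, so a correct tick means that one of three definitions was met; removing two leaves the third. The bleeding definition also turns on cause, which preferred terms such as tachycardia or anaemia cannot show, so investigator judgement has to enter somewhere. This stands as far as it goes. It holds only if every tick is right and the two searches catch every ticked event of their own kind, and the viral search in particular is only two terms wide.

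A reader might infer something stronger: that the rule undercounts thrombosis and viral transmission and inflates bleeding. The documents do not support that. Both searches work without a tick, so they also catch events that the investigator failed to flag, and the bleeding row can lose unticked events. The net direction is unknown. Nor can these events be assumed rare, since no rate is given and Protocol 4.1 calls clinically relevant bleeding a common complication of PMP surgery.

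Much would also be visible. A serology or thrombosis term under the bleeding label shows by name in tables by preferred term, and all adverse events are listed. SAP 12.6.6 gives a shift table for hepatitis B, hepatitis C and HIV whatever the adverse event coding. A separate ischaemic-event search in SAP 12.6.1 would pick up some vascular events. This limits the harm but does not correct the category totals.

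Finally, the eCRF, the coding conventions and the table specifications are separate documents. The eCRF may record the AESI type; if it does, the SAP rule as written does not use it.

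**Conclusion.** The point holds as a minor misclassification in descriptive safety tables. The SAP rule drops the protocol's requirement that bleeding be the cause, and it can put a non-bleeding event in the bleeding row or leave out an unticked bleeding complication. Each affected subject moves a category by about one percentage point overall, and by more within a surgery type. Frequency and net direction cannot be determined from the documents. No hypothesis test and no primary conclusion is affected.

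This rests on reading the SAP table literally and on there being no re-sorting step in the documents that were not available. Confidence is high about the wording of the rule and low about how often it would matter.

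**What to change.** In SAP 12.6.1:

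1. Keep the SMQ and preferred-term searches, because they also catch events that were not ticked.
2. Restrict relevant bleeding complication to events that meet the definition in Protocol 9.3.1. Use the investigator's AESI type if the eCRF records it; otherwise have the leftover ticked AESIs reviewed, blinded to treatment, at the BDRM already planned before database lock.
3. Assign leftover events that are clearly thrombotic or viral to those categories.
4. Show whatever remains in a separate other/unclassified AESI row.

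The investigator's AESI type should supplement the thrombosis search and not replace it, or unticked thromboses would be lost. The cost is SAP wording and a short review list; no new data are needed.
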